9.1.4 Visit 3 (End of the treatment, Day 8 ± 1)

Visit 3 (End of the treatment, Day 8 ± 1) shall be held at the clinical center. The Investigator needs to conduct the following study procedures:

- Collection of patient's complaints;
- Physical examination;
- Measurement of major vital signs (HR, RR, body temperature)
- Symptom Assessment Scale completion

- Checking the diaries completion at home
- Adverse events registration
- Clinical blood test
- Common urine analysis
- Assessment of concomitant therapy
- Assessment of exclusion criteria
- Assessment of compliance with prescribed therapy
- Assessment of the ongoing therapy efficacy by a physician (IMOS scale)
- Assessment of the ongoing therapy efficacy by a parent/adoptive patient (IMOS scale)

On this visit, the patient shall return to the Investigator all the unused and used products. The Investigator shall calculate the returned product, including the antipyretic drug Efferalgan®, and fill in the appropriate form for accounting the study products.

The Investigator, on the basis of data obtained during this Visit, shall make a conclusion about the patient's condition.

If the patient has early terminated the study, he/she should undergo all the procedures provided for this Visit. Upon the completion of all the procedures of Visit 3, the Investigator shall inform the patient about the next visit - Visit 4 (Day 12 ± 1), which will be held through the telephone contact. For the visit, the study physician needs to determine a time convenient for the patient and/or the patient's parents/adoptive parents.

9.1.5 Visit 4 (Study completion, Day 12 ± 1)

Visit 4 (Study completion, Day 12 ± 1) shall be held by telephone contact at a time convenient for the patient and/or parents/adoptive parents. The Investigator needs to conduct the following study procedures:

- Collection of patient's complaints
- Adverse events registration
- Assessment of concomitant therapy
- Study completion.

Upon the completion of all the procedures for Visit 4, the patient, as decided by the Investigator (in the absence of unresolved adverse events), completes the study.

9.1.6. Description of study procedures

Demographic and anthropometric data collection

Demographic data include date of birth, age (number of full years at the time of participation in the study), gender and race. Anthropometric data include weight and height.

Medical history collection

The medical history data includes a description of the underlying disease, including the duration and effect of previously received therapy, a description of previous and concurrent diseases. In addition, information about concomitant therapy shall be collected: INN, trade name, strength, presentation, single and daily dose, date of therapy initiation and termination.

Physical examination

Physical examination includes an examination of the following organs and systems:

- Skin, hair, nails
- Endocrine system
- Cardiovascular system
- Respiratory system, state of nasal passages, character of discharge
- Gastrointestinal tract, including oral examination using a spatula and flashlight
- Nervous system
- Musculoskeletal system
- Reproductive system
- Urinary system

Measurement of vital signs

Measurement of HR, RR shall be performed by qualified medical personnel in accordance with the standards adopted at the study site.

The study is conducted as part of the safety assessment of study subjects.

Body temperature measurement.

It is conducted at screening visits, Visit 1, 2 and 3 by medical personnel, and at home by parents/adoptive patients.

Algorithm for measuring body temperature:

1. Wash your hands with warm water and soap
2. Inspect the armpit, and wipe it dry

3. Take a thermometer and shake off mercury below 35 °C
4. Position the thermometer in the armpit so that the measuring tank is in contact with the body from all sides
5. Measure the temperature for 10 min
6. Pay attention to between the body and the thermometer was no linen
7. Remove the thermometer and record the digital data
8. Shake the thermometer

Parents/adoptive parents should be instructed on how to conduct thermometry at Screening.

ECG

It shall be conducted at suspicion on cardiovascular disease. At least an hour before the procedure, it is necessary to exclude the outdoor games and emotional stress of the child. No less than 1.5 hours shall pass after the meal. In young children, special electrodes are used, which are tightly fixed on the skin without damaging it. Record at least 10–15 cardiac cycles, and if they are suspicion on of arrhythmia, there may be more cycles.

The study is conducted as part of the safety assessment of study subjects.

Laboratory examination

Each clinical center will use its own clinical laboratory to conduct all tests.

Evaluation of the result of a particular indicator will occur taking into account the reference values of local laboratory in each study center.

During the study, the blood and urine samples will be taken to determine the following indicators:

Name of laboratory test	Test items			
Clinical blood test (capillary blood)	Hemoglobin Hematocrit	RBC Platelets	Leukocytes (total and WCC) ESR	
Common urine analysis	Color Clarity	pH Specific weight	Protein Glucose Bacteria	Leukocytes RBC

Express test (on screening only)	
• Influenza virus• Streptococcal infection
---	---

Biological samples will be collected according to the procedures and standards of the clinical center. In the case of taking biological samples at home, the biomaterials will be delivered to the clinical center laboratory under appropriate conditions, using thermal containers with temperature control. The Investigators will be instructed on the rules for transporting biological samples in this study.

The tests shall be conducted as part of the safety assessment of study subjects.

In modern clinical studies practice, in addition to the above laboratory blood tests for the safety assessment of the therapy being conducted, an assessment of biochemical blood parameters shall be performed. In this study, the blood chemistry is impractical for a number of reasons related to the difficult procedure for venous blood collection in patients of the pediatric population, and ethical principles. Due to the fact that Polyoxidonium has been used in pediatric practice for more than 20 years, the accumulated experience of its use suggests that, in the doses used, the product will not have a negative effect on the patient's body.

Urine pregnancy test

The test is carried out on a screening visit and applicable only to female patients with a history of menarche using the certified test strips. The study is conducted as part of the safety assessment of study subjects.

Each clinical center will use its own clinical laboratory to conduct all other tests.

Evaluation of the result of a particular indicator will occur taking into account the reference values of local laboratory in each study center.

Express test for influenza

The test is performed on a screening visit for all patients using certified test strips.

To perform the test, it is necessary to collect biological material that must be examined for influenza virus. This is done by taking the nasal mucus. Use a sterile cotton swab take a smear of nasal epithelium, inserting it into the nasal passage and slightly rotating. Then, follow the patient information leaflet attached to the test system.

The test is conducted as part of the exclusion of influenza virus, which requires specific treatment.

Express test for streptococcal infection

The test is performed on a screening visit for all patients using certified test strips.

To perform the test, it is necessary to collect biological material that must be examined for the streptococcus. To do this, take a swab from the surface of tonsils and the posterior pharyngeal wall using the cotton wool stick supplied with the test system; it is not allowed to touch the tongue, gums, the palate, teeth (with a cotton wool stick (it is sterile). Then, follow the patient information leaflet attached to the test system.

The test is conducted as part of the exclusion of streptococcal infection, which requires specific treatment.

Assessment of compliance with prescribed therapy

Assessment of compliance with prescribed therapy will be conducted on Visits 2 and 3 by checking the Patient's Diary with notes on the amount of product used. A sufficient level of compliance is considered to be the level of compliance with prescriptions over 80% (for more details on tolerances in the treatment regimen, see section 9.4).

9.2 Diagnostic Scales and Patient's Diary

During the study, the patient's condition and the therapy efficacy will be evaluated using the following parameters: 1) "Symptom Assessment Scale" (Appendix 1) - completed by the physician, 2) IMOS scale completed by the physician (Appendix 2) and also by the parent / adoptive parent (Appendix 3).

Symptom Assessment Scale completion will be conducted on Visit 0, Visit 1, Visit 2 and Visit 3. Also, on Day 5 of therapy, in the patient's diary the Symptom Assessment Scale shall be filled in; this procedure will be performed by the parent/adoptive parent. IMOS scale completion (Appendix 3) and assessment of the ongoing therapy efficacy by the patient's parent/adoptive patient (excellent, good, satisfactory, not efficient) will be held on Visit 3.

In addition, parents / adoptive parents of patients will be given a diary to record the patient's body temperature (twice a day: morning and evening), the time of taking the study product / placebo, the time and amount of taking antipyretic (paracetamol) and other drugs and their dosage and method of taking patients' complaints.

The diary and the diagnostic scales completed by the physician are the primary documentation; upon completion of the examination by the patients, they should be collected and kept together with the patient's medical record. When using electronic diaries, the data downloaded from them will be stored in the Investigator's file.

When conducting Visit 1 procedures, the Investigator must train the parents / adoptive parent to fill out a diary. At each visit, the Investigator must verify the correctness and timeliness of filling the diary with the patient's parent / adoptive parent.

9.3 Concomitant therapy

The use of drugs other than those studied (with the exception of the fever-reducing drug Efferalgan®) will be considered as concomitant therapy and will be recorded in primary documentation and in the CRF. The concomitant therapy can include forbidden therapy and authorized therapy.

9.3.1 Forbidden Therapy

The concomitant use of the following medicinal products and/or procedures will lead to the patient's exclusion:

- antiviral drugs;
- immunomodulators (except for the study product);
- antimicrobial agents;
- centrally acting antitussives (butamirate);
- local and systemic glucocorticoids;
- physiotherapeutic treatment.

In the case of taking drugs included in the section "Forbidden therapy", the patient's study participation will be terminated and treatment will continue according to the standard of care for this nosology (treatment will be similar to real clinical practice).

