8.3 Patients' Exclusion

The patient and/or one of the child's parents/adoptive parents may refuse to continue the study participation at any time without explaining the reason and without consequences for the patient's treatment in the future. In this case, the Investigator is obliged to ask the patient to come to the clinical center for the procedures provided for Visit 3 in case of early withdrawal, and also to complete fully, as far as possible, the relevant primary documents and the CRF.

The patient should be excluded from the study directly by the Investigator for the following reasons:

1. Inability or refusal of the patient, his parents/adoptive parents to follow the Protocol's requirements.
2. Informed Consent withdrawal by the patient or his/her legal representative.
3. Requirement for additional therapy is not permitted under this Protocol.
4. Serious adverse events or adverse events that do not meet the severity criteria, that are not categorized as «serious», in cases when further study participation may be pernicious for patients health or well-being, in investigator's opinion.
5. Requirement for surgical intervention.
6. The patient is non-compliant with study procedures.
7. Any patient's condition that reasonably requires withdrawal, in investigator's opinion.

Subjects, who discontinued from the study due to AE/SAE will be under the follow up until total recovery or stabilization of AE.

The emergence of non-inclusion criteria during the study, in general, is not a reason for excluding the patient from the study, as well as new or associated diseases that may affect the course of the study. In these cases, the Investigator must inform the Sponsor / organization conducting the study, which must decide, either alone or with the Investigator, whether to exclude the patient from the study. The patient is eventually excluded from the study or not, the circumstances of exclusion or interruption of participation should be recorded in detail in the primary documentation and in the CRF.

In case of early termination of the study the Investigator should make every effort to ensure the visit of the Completion of the study, which corresponds to the Visit 3 procedures (the visit procedures are described in detail in Section 9.1.4 Visit 3 (end of therapy, day 8 ± 1)).

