9.4 Methods for monitoring compliance with procedures

Compliance of the study product / placebo (adherence to therapy) will be assessed at Visits 2 and 3 according to the patient's electronic diary by checking the data entered by the patient's parent about taking the drug.

On Visit 1, one bottle of the prescribed drug will be given to the patient's parent / adoptive parent.

At Visit 3, the vial of the prescribed drug must be returned by the patient's parent / adoptive parent to the study center.

Monitoring compliance with the protocol procedures during the study is carried out by the investigator

According to the draft Patient information leaflet for Polyoxidonium, during therapy, patients from 1 to 2 years should receive the drug by 1 injection x 2 times per day sublingual (14 drugs in total / 14 doses), patients from 2 to 5 years - intranasal 1 injection in each nasal passage x 2 times a day (14 applications total / 28 doses), patients from 5 to 8 years old - intranasal 1 injection in each nasal passage 3 times a day (21 applications total / 42 doses), patients from 8 to 12 years old - intranasal for 2 injections per each nasal passage 2 times a day (14 applications in total / 56 doses). Possible omissions of taking the drug during the study:

No more than two misses with 2-fold SP / placebo.

No more than four passes - with 3-fold use of SP / placebo.

These conditions will allow maintaining the level of compliance not lower than 80% [21 - 24].

If compliance is less than 80%, patient data will not be included in the efficacy analysis.

Dosage of antipyretic drugs will be assessed during the study according to the Patient's Diary - by checking the completed data by the patient's parent about taking the drug on visits 2 and 3.

On Visit 1, one vial of the prescribed antipyretic drug will be given to the patient's parent / adoptive parent.

On Visit 3, the vial of the prescribed antipyretic drug must be returned by the patient's parent / adoptive parent to the study site.

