All other deviations that are not significant, do not affect the patient's safety and do not substantially violate the procedures provided for by the protocol. Classification of protocol deviations for minor deviations and significant deviations will be made by authorized representatives of the Sponsor after the data on deviations from the Protocol are provided (according to monitoring reports and other sources). A complete list of deviations from the protocol will be approved prior to the start of the statistical analysis and the distribution of patients among the populations for analysis. Deviations from the Protocol are always considered individually with an analysis of the reasons that should be reflected in the primary documentation. The decision to exclude a patient with deviations and violations of the Protocol from the study should be made individually in consultation with the Sponsor of the study.

The decision to include these patients in the statistical analysis is made before closing the database of the study.

If significant deviations from the protocol are found, the patient should be excluded from the final data analysis.

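### Several events end a child's participation in the whole study; with no continued temperature diary and no clear Day 12 contact, the end of fever goes unobserved in a child still febrile at withdrawal

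*Combined protocol and SAP*

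**What the plan says.** **What ends participation**
- Section 9.3.1, on use of a forbidden drug: "the patient's study participation will be terminated and treatment will continue according to the standard of care for this nosology".
- Section 8.3 lists, among the reasons for exclusion from the study, "Requirement for additional therapy is not permitted under this Protocol" (the synopsis makes the sense clear: a need for therapy that the protocol does not allow) and "The patient is non-compliant with study procedures".
- Sections 7.2 and 9.1.3 exclude a child who is judged at Visit 2 (Day 3) to need an antibacterial.
- Section 7.6 obliges the investigator to end participation once an exclusion criterion is met.

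**What is collected afterwards**
- Section 9.1.4: "If the patient has early terminated the study, he/she should undergo all the procedures provided for this Visit". Section 8.3 adds that "the Investigator should make every effort to ensure the visit of the Completion of the study, which corresponds to the Visit 3 procedures".
- Section 8.3: "Subjects, who discontinued from the study due to AE/SAE will be under the follow up until total recovery or stabilization of AE". Section 11.2 keeps any child with an adverse event under supervision until it resolves or stabilises. Section 13.3 does the same after unauthorised drugs given for a threat to life.

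**What conflicts with compulsory withdrawal**
- Section 9.4: "If compliance is less than 80%, patient data will not be included in the efficacy analysis". This removes data from an analysis; it does not order the child out of the study.
- Section 13.3: "The decision to exclude a patient with deviations and violations of the Protocol from the study should be made individually", in consultation with the sponsor.

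**How the endpoint is measured and analysed**
- The end of fever is a temperature at or below 36.9 °C on two readings in a row (section 7.1), taken from a home diary kept morning and evening (section 9.2).
- Efficacy is analysed in per-protocol completers only (section 12.2), and missing data are not filled in (section 12.6).

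**The concern.** For these events, the plan has no status in which a child is off study treatment but still under scheduled observation. The event that changes treatment also ends routine data collection. This differs from the choice of analysis set, which can still be revised before database lock. A temperature that nobody recorded cannot be recovered later.

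The loss is unlikely to be random. Section 5.8 says that increasing fever, or fever that returns after improvement, may point to bacterial infection or otitis. A need for antibacterials is therefore related to the primary outcome. The plan also counts withdrawal for that need as a secondary efficacy criterion, so it allows that the rate may differ between arms. If it does, the children removed are those likely to have long fever, in unequal numbers.

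There is a smaller safety gap. Section 11.2 registers adverse events until the child completes the study. A new event that begins after the completion visit may go unrecorded if the Day 12 call is not made.

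**Working it through.** **1. Can one completion visit supply the endpoint?** The visit yields one clinic temperature and the diary up to that day. If fever ended before withdrawal, the diary already shows it and nothing is lost. If the child is still febrile, dating the end of fever needs two later consecutive readings, and no section provides for them. The first scheduled exclusion assessment is at Day 3. The assumed mean durations are 2.6 and 3.2 days (section 12.1), so some children will still be febrile then.

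**2. Is the Day 12 call kept?** In section 9.1.4, the sentence after the early-termination rule says that, once the Visit 3 procedures are done, the patient is told about Visit 4. Section 8.3 and the synopsis call the early visit the completion visit. The text can be read either way. Visit 4 takes no temperature in any case (section 9.1.5, Appendix 5).

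**3. The plan's own figures.** Inputs from section 12.1: Z values 1.645 and 0.842, SD 0.2, means 2.6 and 3.2, δ = −0.52.
- Distance beyond the decision limit: |2.6 − 3.2 + 0.52| = 0.08 day.
- n = (1.645 + 0.842)² × 2 × 0.2² / 0.08² = 77.3, rounded up to 78 per arm. The stated figure reproduces.
- The synopsis allows 10% dropout and randomises 86 per arm. A 10% loss is 0.10 × 172 = 17.2 children. It leaves 77 per arm with 79.9% power (one-sided 0.05, plan's inputs). The loss of numbers is provided for; selective loss is not.

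**4. Size of a selective loss (assumed inputs).** If w of an arm's 86 children are lost, and their fever would have lasted d days longer than in that arm's remaining children, the arm mean falls by w × d/86. With the same d in both arms and a between-arm imbalance of k children, the difference moves by k × d/86.

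| Imbalance k | Extra days d | Shift (days) |
|---|---|---|
| 3 | 2 | 6/86 = 0.070 |
| 4 | 2 | 8/86 = 0.093 |
| 7 | 1 | 7/86 = 0.081 |

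The shift exceeds 0.08 day once k × d is above 0.08 × 86 = 6.88 child-days. As a range, losing 5% to 10% of one arm only, with 0.5 to 2 extra days, moves that arm's mean by 0.05 × 0.5 = 0.025 to 0.10 × 2 = 0.20 day.

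**5. Direction.** Start from a full-data difference of −0.60. If placebo loses 4 more such children, the remaining children show −0.60 + 0.093 = −0.507, short of −0.52. If the active arm loses 4 more, they show −0.60 − 0.093 = −0.693, and the benefit is overstated.

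**The case against.** A reader might infer that temperature and safety data after withdrawal are never collected. The documents do not support that. Every early withdrawal calls for a completion visit with temperature, symptom scale, diary check, adverse events, blood and urine tests and the outcome scale. The definition of an adverse event in section 11 is wide enough to cover a new bacterial complication. Section 11.2 then requires supervision until it resolves, whatever reason for withdrawal was recorded. The safety gap is therefore narrow.

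A reader might also infer that stopping the product by itself means leaving the study. It is not a listed reason in section 8.3. For a serious adverse event, section 11.2 has the child stop the drug but remain under supervision. Low compliance and protocol deviations are not uniformly tied to withdrawal either.

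Three further objections have weight:
- **The illustration is assumed.** The documents give no withdrawal rate by arm and no fever duration for withdrawn children. Two extra days is ten of the plan's own SDs (2/0.2). Its only support is section 5.8, which mentions fever of up to 5–7 days in influenza and adenovirus infection, and influenza is screened out by express test. Section 5.8 also says temperature falls by day 2–3 in 82% of patients, so many withdrawn children may have a complete endpoint.
- **The bias need not favour the product.** If placebo loses more long-fever children, the benefit shrinks.
- **More diary data would enter no planned efficacy analysis**, because only per-protocol completers are analysed.

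All three stand as limits. The first two bound the size and direction of the effect without removing it. The third means that the data-collection change needs an analysis that uses the data.

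**Conclusion.** The point holds in this form. Forbidden or non-permitted therapy, an antibacterial need at Visit 2 and non-compliance with procedures end participation in the whole study. Beyond one completion visit and adverse-event follow-up, the plan provides no continued temperature diary and no clear Day 12 contact. For a child still febrile at withdrawal, the end of fever is unobserved, and the reason for withdrawal can be related to that outcome.

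The size is uncertain. It rests on assumed imbalances and assumed extra fever days, and the shift can go either way. It matters because the margin for error is small: a net 6.88 child-days is enough to equal the 0.08 day between the assumed effect and the decision limit. The documents do not show that bias will occur, or that it would favour the product. The change is worth making because it is cheap and the missing temperatures cannot be recovered afterwards.

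**What to change.** 1. In sections 8.3, 9.1.3 and 9.3.1 (and the matching text in 7.2), separate the end of study treatment from withdrawal from data collection. Unless consent is withdrawn, the child keeps the diary to Day 8 ± 1, has Visit 3 as scheduled and receives the Visit 4 call, and the new treatment is recorded. The existing rules on product and care stay as they are.
2. In sections 12.2 and 12.3, add an as-randomised analysis of fever duration that uses these temperatures, reported beside the per-protocol analysis. State how a child still febrile at the last diary entry is counted. Without this step, the added temperatures would not affect any planned efficacy result; later adverse events would still enter the planned safety analysis.
3. Reconcile sections 7.6, 8.3, 9.3.1, 9.4 and 13.3 on which events mean leaving the study and which mean leaving the efficacy analysis only.
4. State in section 9.1.4 whether Visit 4 applies after early termination.

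The cost is protocol wording and one added analysis, since the diary, visit and call already exist. Some families will decline to continue the diary, so the loss will be reduced but not removed.
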